Based on our working hypothesis that opioid receptor blockade might arrest antipsychotic induced weight gain, we have conducted a pilot 8 week randomized, double blind, placebo controlled, parallel, fixed dose clinical study of naltrexone (25mg) for treatment of weight gain in schizophrenia. The study was supported by Women's Health Research at Yale and only obese women with clinically stable schizophrenia who had gained over 2% of their TBW in the previous year were recruited. Substance abuse and pregnancy were the major exclusion criteria. Over a period of one year, 29 volunteers were screened, and 24 subjects were randomized to 25 mg oral naltrexone or matching placebo for a period of 8 weeks. No diet advice or behavioral weight loss intervention was provided. No subjects reported joining an outside program at the end of the study. One subject in the placebo arm dropped out at the fourth week due to personal reasons, all remaining subjects completed the 8 week trial. No serious adverse effects were reported and study medicines were well tolerated. At the end of the study, subjects who were randomized to active naltrexone arrested the weight gain, with a further average reduction of 2.45 kg as opposed to subjects who were randomized to placebo, who continued to gain weight at an average of 0.47kg (Figure 3). The difference between two groups closely approached significance at $p=0.051$, and produced a power of $d=0.59$. Baseline weight was not correlated with weight change in the study. On the other hand, exploratory analyses revealed that diabetes was a confounding factor, and only non-diabetic subjects on naltrexone lost significant weight compared to placebo subjects (non-DM **-4.98kg** (± 3.03) vs. DM - **.27** (± 3.05),Figure 3). It was also discovered that the intensity of craving for sweets as measured by the Questionnaire of Cravings for Sweet and Rich Foods (QCSR) was significantly reduced for the NTX group and unchanged for the placebo. Unfortunately the study was underpowered, as expected from a pilot study, and provides no information on naltrexone effects on males. In spite of these limitations, our study provides important information. Given that obese patients with chronic schizophrenia typically continue to gain weight at a clinically significant level, this pilot is unique among other studies, and its results must be interpreted within this

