Subjects will be randomized to active Naltrexone 25mg, Naltrexone 50mg, and placebo groups in a 1:1:1 ratio using a computer randomization procedure at the CMHC research pharmacy, blind to both research team and subjects. Separate randomization schedules will be applied based on gender, and antipsychotic agent to yield an equal number of male and female subjects in each arm. This is to control for possible differential gender and racial/ethnicity specific effects of Naltrexone on weight as well as differences brought on by higher and lower weight liability medications.

Subjects will take the study medication daily for 52 weeks. Subjects will be seen weekly for the first 4 weeks of the study, thereafter they will be seen on a bi-weekly (every other week) basis to be assessed (i.e. weight, side effect check, paper questionnaires) throughout the remaining 48 weeks of treatment. Compliance will be monitored by pill counts as well as 25mg riboflavin added to the capsules which provides florescence to urine under Wood's lamp (UV or black light). Subjects will be given a study identification card listing the fact that they may be taking naltrexone and this card will include the study emergency cell phone number which will be available 24 hours a day, 7 days per week in case of an emergency.

The study is planned to be run at the Connecticut Mental Health Center (CMHC) and its affiliated satellite clinics throughout the greater New Haven area.

All participants will be carefully assessed with physical examination and laboratory findings, any medical problems that need immediate attention will be referred to each participant's own primary care physician. All potential subjects will meet with study staff for intake and evaluation sessions to determine eligibility prior to enrollment.

A description of assessments is given below:

1) Intake interview including demographics, clinical history, Structured Clinical Interview for DSM-IV (**SCID**) to ascertain diagnosis. 2) Urine toxicology (**Utox**) screen to rule out substance use. The initial sample will also be sent to the lab to confirm opiate results for safety purposes and a follow-up sample will be taken immediately before randomization to study medication to ensure it is negative for opiates; continued random testing will occur at the discretion of the study physician throughout the trial along

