Data will be electronically scanned into databases and will be double checked by hand. Hard copy documents will be examined to verify questionable observations. Missing data will be examined for each variable. Histograms, normal probability plots, and numerical summaries (skewness, kurtosis) will be used to examine distributional assumptions required for the mixed model analysis described below. Transformations such as the logarithm, square root, and reciprocal will be considered in the event the normality assumption is inadequate. Residual analysis will also be performed to evaluate distributional variance and linearity assumptions. Data analysis will be conducted in collaboration with [name], statistician in the department of Psychiatry and [name] faculty member of the Department of Biostatistics at Yale University School of Public Health. For all analyses, an alpha threshold of 5% (two-sided) will be used to test for statistical significance and will be performed using SAS v9.3 (SAS Institute, Cary, NC).

Analyses will be performed according to the intent-to-treat (ITT) principle where data from any randomized subjects will be analyzed. We will calculate descriptive statistics for participants at baseline, and compare naltrexone to placebo participants using analysis of variance (ANOVA) for normally distributed covariates and chi-square tests for categorical covariates. The impact of baseline variables that demonstrate clinically relevant group differences will be assessed in supportive analyses using covariate adjustment.

Approach to Missing Data: The primary analysis method will use a likelihood-based mixed model, which accommodates incomplete observations and operates under the assumption that the missing data is missing at random (MAR). Missing data patterns, time to withdrawal and reasons for dropout will be compared between the two naltrexone and placebo groups. T-tests, cross-tabulations, and logistic regression will be used to evaluate whether withdrawal is dependent on any observed variables. Finally, should missing data patterns and reasons for missing data suggest a bias or confounding, we will conduct sensitivity analyses using pattern mixture models to examine the influence that dropout bias (informative missingness) may have on treatment differences. Multiple imputation (MI) will also be used in the case of data not MAR. Sensitivity analyses will be performed secondarily among study completers.

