Hypothesis Testing: The primary goal of this study is to compare the weight changes resulting from two different doses of naltrexone compared to placebo. The primary ITT analysis will employ a linear mixed effects model (LMM) to determine the effect of treatment status (between-subjects for: naltrexone 25/50mg vs. placebo) on the trajectory of weight change over time (within-subjects for: study time points). The interaction between treatment and time will be modeled and interpreted using graphical displays and post-hoc contrasts on least square means. The latter will include estimation of group contrasts at each time point and polynomial (linear, etc.) contrasts for time within each group. However, the primary contrasts will be each dose compared with control at 52 weeks. Because the outcome data are correlated (i.e., weight assessed from the same subject at different time points), weight over time will be modeled through the inclusion of random subject effects and/or structured variance-covariance matrices, with the best-fitting structure determined by Bayesian-Schwartz Information criteria (BIC). Supportive analyses will also include covariate adjustment for clinically significant variables (as determined from baseline evaluations and also other treatment variables, such as sessions attended). The above model will be fit using SAS PROC MIXED (Cary, NC), using restricted maximum likelihood (REML). The effect of treatment assignment on the secondary outcomes, such as BMI, waist circumference, serum lipid profile, fasting glucose, and glycosylated hemoglobin (HbA1c) will be evaluated using the linear mixed modeling approach described above. The proportion of subjects achieving 3, 4, or 5% weight loss will be compared between the treatment groups with the Fisher's Exact test. Type 1 error for secondary outcomes will be adjusted using the Bonferroni correction, basing the adjustment on the number of conceptually related statistical tests.

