SECTION VII: RECRUITMENT/CONSENT AND ASSENT PROCEDURES

1. Targeted Enrollment: Give the number of subjects:

a. targeted for enrollment at Yale for this protocol 200

b. If this is a multi-site study, give the total number of subjects targeted across all sites N/A

2. Indicate recruitment methods below. Attach copies of any recruitment materials that will be used.

- Flyers
- Posters
- Letter
- Medical Record Review
- Departmental/Center Newsletters
- YCCI Recruitment database
- Other (describe): Clinician Referrals

- Internet/Web Postings
- Mass E-mail Solicitation
- Departmental/Center Website
- Departmental/Center Research Boards
- Web-Based Clinical Trial Registries
- Clinicaltrials.gov Registry (do not send materials to HIC)

- Radio
- Telephone
- Television
- Newspaper

3. Recruitment Procedures:

a. Describe how potential subjects will be identified.

Potential subjects will either self-identify by seeing a flyer and contacting us with their interest, or their clinician may identify them as potentially eligible and give them our contact information. Familiar patients who have done multiple studies with us or who are patients of [name] may be identified by research staff as potentially eligible.

b. Describe how potential subjects are contacted.

Potential subjects will contact research staff in order to complete a telephone screening procedure that will determine eligibility. At that point, we will get permission from the patient to contact them further about the study, via telephone or through their clinician. If a potential subject has been in one of our studies in the past and has given permission to be contacted about future studies, research staff will call them to see if they are interested.

c. Who is recruiting potential subjects?

[name], [name], [name], [name], [name], [name]

4.

Screening Procedures

- a. Will email or telephone correspondence be used to screen potential subjects for eligibility prior to the potential subject coming to the research office? Yes No
- b. If yes, identify below all health information to be collected as part of screening and check off any of the following HIPAA identifiers to be collected and retained by the research team during this screening process.

HEALTH INFORMATION TO BE COLLECTED:

HIPAA identifiers:

- Names

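### Randomization is stratified by gender and antipsychotic agent, but the primary mixed model names neither factor; adding them by time is a free gain in precision

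*Combined protocol and SAP*

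**What the plan says.** **Randomization.** Section V, item 3 (Research Plan) allocates subjects "in a 1:1:1 ratio using a computer randomization procedure" and adds: "Separate randomization schedules will be applied based on gender, and antipsychotic agent". The first reason given is "This is to control for possible differential gender and racial/ethnicity specific effects of Naltrexone on weight". The second is that antipsychotics differ in their liability to raise weight. The levels of the antipsychotic factor are not defined, and race/ethnicity is not a factor.

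**Primary model.** Section V, item 12, Hypothesis Testing, uses a linear mixed model "to determine the effect of treatment status (between-subjects for: naltrexone 25/50mg vs. placebo" as the between-subject term, with study time points within subject and a treatment-by-time interaction. The primary contrasts are each dose against placebo at week 52. Neither gender nor antipsychotic agent is named as a model term.

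**Covariate adjustment.** It appears twice in item 12, both times as supportive. One place ties it to baseline variables that show clinically relevant differences between groups. The other refers to clinically significant variables identified from baseline evaluations or treatment. Neither names the strata.

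**Gender.** The Background (Section V, item 2) says that the pilot "provides no information on naltrexone effects on males". The analysis section plans no estimate by gender and no treatment-by-gender term.

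**The concern.** A trial that randomizes within strata would ordinarily analyse with those strata in the model. Stratification makes the arms more alike on gender and antipsychotic than simple randomization would, so the treatment contrast varies less from one randomization to the next. A model without the strata does not know this. It leaves the variance they explain in the residual and reports a standard error that is too wide. Precision that the design has already paid for is then lost in the analysis.

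The first trigger for supportive adjustment makes it unlikely that the strata would come in that way, because it asks for a baseline difference between groups, which is what stratification is there to prevent.

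There is also a wording problem. The rationale claims control of race/ethnicity effects, and nothing in the randomization or the analysis provides it.

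**Working it through.** The plan attaches no figure to this point, so there is none to reproduce. The documents give no SD, target difference, dropout or variance explained by the strata. The figures below are illustrations on stated assumptions.

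**Inputs from the documents**
- Total sample: "targeted for enrollment at Yale for this protocol 200" (Section VII, item 1). Three equal arms give 200/3 = 66.7 per arm.
- Test level: "an alpha threshold of 5% (two-sided) will be used to test for statistical significance" (Section V, item 12).

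**Assumed:** R², the share of variance in weight change explained by the strata, between 0.02 and 0.20, with arms balanced within strata and no dropout.

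**Step 1. Cost of leaving the strata out.** The reported standard error is too large by the factor k = 1/√(1 − R²). The true size of the nominal 5% test is 2(1 − Φ(1.96k)).

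| R² | k | 1.96k | True size |
|---|---|---|---|
| 0.02 | 1.010 | 1.980 | 4.8% |
| 0.05 | 1.026 | 2.011 | 4.4% |
| 0.10 | 1.054 | 2.066 | 3.9% |
| 0.20 | 1.118 | 2.191 | 2.8% |

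**Step 2. What this means for power.** With 66.7 per arm, the difference detectable with 80% power when R² = 0 is (1.960 + 0.842) × √(2/66.7) = 0.485 SD. At that difference, power without and with the strata in the model is 0.802 and 0.807 for R² = 0.02, 0.81 and 0.84 for R² = 0.10, and 0.83 and 0.88 for R² = 0.20.

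**Step 3. In what form the strata must enter.** The response is weight over time. A stratum term that is constant over time adds the same amount to a subject's baseline and week-52 weight, so it cancels from the change and leaves the residual variance of change as it was. A simulation shows this (66 per arm, one balanced binary stratum with R² = 0.20 for change, baseline kept as a response, unstructured covariance, 1,500 runs; true SD of the contrast 0.933):

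| Model | Mean reported SE of week-52 change contrast | Test size |
|---|---|---|
| No stratum | 1.048 | 3.3% |
| Stratum, constant over time | 1.048 | 3.3% |
| Stratum by time | 0.933 | 5.5% |

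The ratio 1.048/0.933 = 1.12 agrees with step 1. If the contrast is instead on week-52 weight itself, a constant term does help, but the relevant R² is then that for weight. Stratum-by-time terms serve both readings.

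**Step 4. What a gender estimate could deliver.** Assume an even gender split and no dropout, so 33.3 per arm and gender. For one dose against placebo:
- Main contrast: SE = √(2/66.7) = 0.173 SD.
- Treatment-by-gender contrast: SE = √(4/33.3) = 0.346 SD, twice as large, with a 95% half-width of 1.96 × 0.346 = 0.68 SD.
- Dose effect within one gender: 95% half-width of 1.96 × √(2/33.3) = 0.48 SD.
- Power for an interaction of 0.59 SD (the pilot's reported d, used only as a yardstick): about 0.40, or about 0.35 at a 30:70 split.

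Such a contrast can be reported as an estimate with an interval, but is a weak test.

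**The case against.** The strongest objections, and what stands of each:

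- **The error is in the safe direction and its size is unknown.** This stands. There is no bias and no inflation of type I error. R² may be small: subjects must be three months past an antipsychotic switch (Section V, item 7), and at R² = 0.02 the loss is about 1% of the standard error. The range in the working starts at 2% for that reason.
- **Supportive adjustment could take the strata in.** This stands in part. The wording in Hypothesis Testing about clinically significant variables is broad enough to include gender and antipsychotic. But it does not name them, and it does not reach the primary analysis.
- **Balance by gender does serve a purpose.** This stands. A reader might infer that stratifying by gender does nothing about a gender-dependent drug effect. That goes too far: if the effect differs by gender, unequal gender mixes would distort the comparison of 25 mg, 50 mg and placebo, and balance guards against it. Balance does not estimate the difference, but the plan does not say that it does.
- **No aim concerns gender.** This stands. A reader might infer that stratification was meant to show whether the women-only pilot result carries over to men, so that a promised analysis is missing. The documents do not say so. The hypotheses and the exploratory aim in Section V, item 1 do not mention gender, and the pilot's lack of men is listed only as a limitation.

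**Conclusion.** This is a free improvement, not a flaw that threatens the result. The trial randomizes by two factors that its primary model does not name. The week-52 contrasts remain unbiased, with standard errors about 1% to 12% too large and true test size about 4.8% to 2.8%, if the strata explain 2% to 20% of the variance in weight change. That range is assumed, as are good balance within strata and no dropout.

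A reader might infer that the primary analysis is invalid or its error rate inflated. Neither follows, since the tests are conservative. A reader might also take the antipsychotic stratum to be a two-level split into higher and lower weight liability. The plan randomizes by agent and mentions liability only in the rationale, so the levels are open.

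The race/ethnicity wording is a minor mismatch between rationale and design. An analysis by gender is optional.

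**What to change.** 1. In Section V, item 12, add gender and the antipsychotic stratum to the primary mixed model as fixed effects with stratum-by-time terms. Alternatively, model week-52 change with the strata as covariates.
2. In Section V, item 3, state the levels of the antipsychotic factor, and use the same levels in the model as in the randomization schedules.
3. Remove race/ethnicity from the stated purpose of stratification.
4. Optionally, report the week-52 dose effects by gender, with the treatment-by-gender estimate and confidence interval, labelled supportive and low-powered.

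The cost is wording. Both factors must be known at randomization, so no new data, visits or subjects are needed. The one practical burden is extra parameters: weight is measured at 4 weekly and then 24 two-weekly visits, so with time as categories each added stratum level brings 28 by-time terms (4 + 24). If the antipsychotic factor has many sparse levels, a pooling rule should be fixed before unblinding.

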with medication compliance procedures; and pregnancy tests for female subjects as it may not be advisable for pregnant women to lose weight. 3) Weight (**Wt**) measurement to the nearest 0.5kg and height (**ht**) will be measured to calculate **BMI**. Waist circumference (**WC**) will be measured with a tape measure placed on the midpoint between iliac crest and lowest rib rounded to the nearest 5 mm. Resting blood pressure (**bp**) and pulse will be measured. Our lab has established procedures for calibrating scales (National Institutes of Standards and Technology Certified weights) and waist measurement. The lab conducts reliability exercises for waist measurements for study stuff (ICC= 0.97, TEM=2.4%) 4) Standard Laboratory Testing (**Lab**) 5) Brief Psychiatric Rating Scale (**BPRS**) is the gold-standard overall measure of schizophrenia symptoms which will be utilized to demonstrate that the Naltrexone and/or SIMPLE intervention does not cause worsening of the illness symptoms apart from the usual fluctuations of the natural course. 6) Beck Depression Inventory (**BDI**) 21-item version is a psychometrically sound, widely used measure of the features and symptoms of depression. The BDI taps a broad range of negative affect – not just depression – and is a highly efficient measure for detecting fluctuations in broad psychopathology and distress. 7) Three Factor Eating Questionnaire (**TFEQ**) also known as the Eating Inventory is a measure of eating behaviors with three factors: dietary (cognitive) restraint, disinhibition, and hunger. The TFEQ has received psychometric support and is a frequently used measure in obesity trials. 8) The Questionnaire on Craving for Sweet or Rich Foods (**QCSR**) The QCSR is a two factor, nine item scale assessing the presence of cravings for rich and sweet foods and has been found to have good psychometric properties. 10) The Yale Physical Activity Survey (**YPAS**) is an interview-administered questionnaire that assesses activity participation in number of hours/week in different categories (i.e. work, recreation, exercise) and takes about 20 minutes to complete. 11) Resting Metabolic Rate (**RMR**) is calculated through a mathematical formula not indirect calorimetry. No special procedure is utilized that would be bothersome to subjects. 12) Quality of Life Enjoyment and Satisfaction Questionnaire (**Q-LES-Q**) is specifically designed to use with schizophrenia patients and focuses on patient's subjective perception of various aspects of their life. 13) SF-36 Health related Quality of Life Questionnaire; a 36-item short-form (**SF-36**) was constructed to survey health status in the Medical Outcomes Study. The SF-36 was designed for use in clinical practice and research, health policy evaluations, and general population surveys. The SF-36 includes one multi-item scale that assesses eight health concepts: 1. limitations in physical activities because of health problems; 2. limitations in social activities because of physical or emotional problems; 3. limitations in usual role activities because of physical health problems; 4. bodily pain; 5. general mental health (psychological distress and wellbeing); 6. limitations in usual role activities because of emotional problems; 7. vitality (energy and fatigue); and 8. general health perceptions. SF-36 can be administered as a self-rating scale or by interviewer. In this study, trained rates will administer the SF-36. 14) UKU Side Effect Checklist (**UKU**) This is a comprehensive rating scale developed for psychotropic drugs and a cross-sectional study of side effects in neuroleptic-treated patients. Common adverse events related to naltrexone will be added to this scale, as needed. 15) Columbia-Suicide Severity Rating Scale (**C-SSRS126**) is a scale developed for use in clinical trials of psychoactive agents and recommended by the FDA to be used for safety tracking of medications for suicidality. 16) Cognitive Battery. Tests from the Measurement and Treatment Research to Improve Cognition in Schizophrenia (**MATRICS**) Consensus Cognitive Battery (**MCCB**): Given the cognitive impairment of schizophrenia, careful assessment of cognition is necessary for feasibility of any medication use in schizophrenia. This is a cognitive battery developed on NIMH initiative by experts from academia, pharmaceutical industry, and US government for the specific purpose of use in clinical trials in schizophrenia. Validity, reliability, sensitivity to change, and normative data is established.

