Other Outcomes: Schizophrenia symptoms (BPRS), depression (BDI), dietary consumption (TFEQ), exercise (YPAS), quality of life (Q-LES-Q and SF-36), cognition (MATRICS) and metabolism/inflammation markers will be obtained as presented in table 3. Summary statistics (frequencies, percents, means and standard deviations, and medians and interquartile ranges) will be calculated for naltrexone vs. placebo at each time point. Appropriate parametric (for normally distributed data) and non-parametric (deviation from normality in data distribution) approaches will be used to ascertain clinically meaningful group differences at each time point. Depending upon the distribution of these outcomes, the effect of naltrexone vs. placebo on change over time in each outcome will also be examined with GLMM, making appropriate model selections for either binary or continuous outcomes.

Using UKU Side Effect Checklist and C-SSRS we will list and summarize side effects and suicidal tendencies reported in each treatment group. Medication changes that could not be avoided during the study will be examined in three groups: no change, change from a higher weight liability to a lower weight liability medication, and vice versa. Weight liability rankings of antipsychotics will be based on Allison and Newcomer. Distributions of all variables will be evaluated for normality. Alternative statistical approaches such as transformations or non-parametric tests will be used, as required.

SECTION VI: RESEARCH INVOLVING DRUGS, BIOLOGICS, RADIOTRACERS, PLACEBOS AND DEVICES

A. DRUGS, BIOLOGICS and RADIOTRACERS

- 1. Identification of Drug, Biologic or Radiotracer:** What is (are) the name(s) of the drug(s) biologic(s) or radiotracer(s) being used? Identify whether FDA approval has been granted and for what indication(s).

Naltrexone is an FDA approved medication with the indication of alcohol dependence.

All protocols which utilize a drug, biologic or radiotracer **not** approved by, but regulated by, the FDA, or a radiotracer regulated by the RDRC, must provide the following information:

- a. What is the Investigational New Drug (IND) **number** assigned by the FDA? N/A
- b. Who holds the IND?
- c. All protocols which utilize a radiotracer not approved by, but regulated by the FDA must provide the IND number: _____
Alternatively, use of the investigational radiotracer may be under RDRC/RSC oversight: (check if appropriate) _____

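### The BPRS is meant to demonstrate no worsening of illness symptoms, but the planned difference tests, without a margin or confidence-interval criterion, cannot show that

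*Combined protocol and SAP*

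**What the plan says.** In Section V, item 3 (Research Plan, assessment 5), the BPRS is introduced as the scale that will demonstrate that naltrexone, or the SIMPLE intervention, "does not cause worsening of the illness symptoms apart from the usual fluctuations of the natural course". No number is attached to the closing qualifier about usual fluctuations.

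Section V, item 12 (Statistical Considerations) places the scale in the paragraph that opens "Other Outcomes: Schizophrenia symptoms (BPRS), depression (BDI), dietary consumption (TFEQ", so it is neither the primary outcome nor one of the secondary outcomes named under Hypothesis Testing. Three things are planned for it:

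- summary statistics by group at each time point;
- parametric or non-parametric "approaches will be used to ascertain clinically meaningful group differences at each time point";
- a longitudinal model: "the effect of naltrexone vs. placebo on change over time in each outcome will also be examined with GLMM".

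The general rule earlier in the same item is: "For all analyses, an alpha threshold of 5% (two-sided) will be used to test for statistical significance".

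The Assessment Schedule has the BPRS at week 0 and every 4 weeks. The documents give no BPRS margin, SD or power figure, no threshold for a clinically meaningful difference, and no statement of how a non-significant BPRS result will be interpreted.

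**The concern.** Showing that a treatment does not worsen something is a non-inferiority type of aim: the data must rule out a worsening larger than some stated amount. A test of zero difference asks something else. When it fails to reject, the data may be compatible with no effect, or with a worsening that the trial was too small to detect. The only decision rule that applies to the BPRS is the two-sided 5% threshold, so the plan offers no route from its analysis to the conclusion it states.

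The participants are antipsychotic-treated patients with severe mental illness, required to be symptomatically stable at entry, who take an opioid antagonist or placebo for 52 weeks. A statement that naltrexone does not worsen illness symptoms could influence later use. It should rest on how large a worsening the data exclude.

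**Working it through.** **Aim against analysis.** The aim in item 3 is to demonstrate no worsening beyond usual fluctuation. The tools in item 12 are summaries, difference tests and a GLMM at two-sided 5%. To connect the two, the plan would need a margin, or a rule based on the confidence limit. Neither is present. The reference to clinically meaningful differences does not supply one, because no threshold is defined. The mismatch needs no arithmetic.

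**Size, for illustration.** The plan has no BPRS figure to reproduce. The inputs are:

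- N = 200 (Section VII, item 1) at 1:1:1 (Section V, item 3): 200/3 = 66.7, taken as 66 per arm.
- SD of the BPRS: not given, so results are in SD units, with a positive difference meaning worse.
- True worsening of 0.2 to 0.5 SD, and dropout of 0% to 40%: assumptions.
- One visit, unadjusted, one dose versus placebo.

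SE = √(2/66) = 0.174 SD. The 95% CI half-width is 1.98 × 0.174 = 0.344 SD. A result just short of significance has an estimate near 0.344, so its interval reaches about 0.344 + 0.344 = 0.69 SD of worsening.

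The probability that a true worsening d is non-significant is approximately Φ(1.96 − d/SE). The first row below is the t-test version. The others use the normal formula, which differs by about one percentage point.

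| Comparison | 0.2 SD | 0.3 SD | 0.4 SD | 0.5 SD |
|---|---|---|---|---|
| One dose, 66 per arm, no dropout | 79% | 60% | 37% | 19% |
| One dose, 20% dropout (53.3 per arm) | 82% | 66% | 46% | 27% |
| One dose, 40% dropout (40 per arm) | 86% | 73% | 57% | 39% |
| Pooled doses, 133 vs 67, no dropout | 73% | 48% | 24% | 8% |

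Baseline adjustment multiplies the SD by √(1 − r²). With an assumed r of 0.5 to 0.7, a 0.3 SD worsening at 66 per arm is missed about 49% to 33% of the time.

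**What a margin would require.** With a true difference of zero and one-sided 2.5%, power is Φ(margin/SE − 1.96), and the n per arm for 80% power is 2 × (1.96 + 0.842)² / margin². The power columns use 66.7 and 53.3 per arm.

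| Margin | Power, no dropout | Power, 20% dropout | n per arm for 80% |
|---|---|---|---|
| 0.2 SD | 21% | 18% | 393 |
| 0.3 SD | 41% | 34% | 175 |
| 0.4 SD | 64% | 54% | 99 |
| 0.5 SD | 82% | 73% | 63 |

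**The case against.** The sentence about the BPRS is an instrument description, in a section whose form asks for non-technical language. The Statement of Purpose lists two hypotheses and an exploratory aim, none about the BPRS. The sentence also names a SIMPLE intervention that is not one of the three randomised arms, so it is loosely worded. The planned analysis is wider than one test: it includes summaries at each visit and a model of change over time, and nothing bars confidence intervals. Other safety monitoring surrounds the BPRS: the BDI and C-SSRS every 4 weeks, the UKU weekly and then every two weeks, adverse event reporting, and DSMB review twice a year. The psychiatric risks that the protocol names for naltrexone are depression and suicidality, which are followed with other instruments.

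Most of this stands, and it limits the weight of the point. It does not remove the mismatch. The protocol assigns the no-worsening statement to the BPRS, describing it thus: "Brief Psychiatric Rating Scale (BPRS) is the gold-standard overall measure of schizophrenia symptoms". The other instruments do not rate overall illness symptoms, and allowing an interval is not the same as saying that the conclusion will rest on it.

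A reader might infer that a non-significant BPRS result will be reported as evidence of safety. No sentence in the documents says so. A reader might also infer that a moderate worsening would usually be missed. That depends on the assumptions: it is true at 0.3 SD for a single dose without adjustment, but not at 0.4 or 0.5 SD without dropout, nor at 0.3 SD with the doses pooled or with the baseline adjustment shown, absent dropout.

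**Conclusion.** The concern holds in a limited form: the stated purpose of the BPRS is a demonstration of no worsening, and the analysis given for it cannot provide one. Severity is modest, because the BPRS is an other outcome outside the hypotheses and is not the only psychiatric safety measure.

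The size depends on assumed effects, assumed dropout and a single unadjusted visit. On those terms, one dose versus placebo is estimated to within about ±0.34 SD, and worsenings of 0.2 to 0.3 SD would more often than not be non-significant. Dropout raises the miss rates. Pooling the doses or adjusting for baseline lowers them, and the gain from repeated measures cannot be computed from the documents. The logical gap does not depend on any of these figures.

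**What to change.** In Section V, item 12 (Other Outcomes), state that the BPRS conclusion rests on the estimated difference and 95% confidence interval for each dose minus placebo at week 52 from the longitudinal model, and that p > 0.05 will not be reported as no worsening. This uses the same contrast as the primary weight analysis and settles whether the doses are compared separately. In Section V, item 3, change *demonstrate* to *estimate*.

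The cost is a few sentences and no new data, since the BPRS is already collected every 4 weeks. The downside is a more modest safety statement.

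If a formal no-worsening claim is wanted, set and justify a margin in BPRS points before unblinding and judge the upper confidence limit against it. The plan should then acknowledge that, on the unadjusted single-visit calculation, N = 200 gives about 80% power per dose only for a margin near 0.5 SD and only without dropout. Rewording is therefore the realistic default.
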